12.3 Motivation for outcome measures

To date, in most studies evaluating invasive treatments in advanced PD, the outcome is based on the recording of PD symptoms with the MDS-UPDRS, the time being in ONphase, the level of physical disability or perceived quality of life as measured with the PDQ-39. The mechanisms of action and procedures of both therapies are very different. For example, DBS treatment includes neurosurgery, implantation of stimulation equipment, and tuning of DBS-parameters in combination with gradual adjustments of the medication-schedule. In DBS, OFF-phase symptoms improve; and patients may experience this as more ON-phase time. DBS may influence behaviour and mood. In case of CLI, patients have a percutaneous endoscopic gastrostomy (PEG). During chronic CLI treatment, the pump has to be started every morning, it has to be removed every night, the PEG-stoma needs continuous care, and there is no change regarding OFF-phase symptoms, but OFF-phase time decreases and ON-phase time increases. The pump weights 0.5 kg. Considering all these aspects and patients' preferences, using OFF-phase parkinsonism, time being in ON-phase, or physical disability as a primary outcome would be inadequate. Therefore we have chosen to use patient-reported perceived quality of life -- measured with the PDQ-39 -- as a primary clinical outcome and as the effect measure to be linked with costs in the cost-effectiveness analysis. In addition, the cost per QALY was chosen as the outcome measure of the cost-utility analysis to allow for comparisons of results from economic evaluations of different interventions within and across different disease populations and different health sectors. The EQ-5D will be applied as the utility measure.

Version 7: 23-10-2019 42 of 48

12.4 Assessment schedules

	Visit 1 Baseline	Visit 2	Visit	Visit 4	Visit 5	Visit 6	Visit	Visit 8
	Daseille	1wk	3mo	6mo	9mo	12mo	, 24mo	36mo
Baseline characteristics	X							
EKG, CT/MRI brain	X							
blood analysis	Х					Х		
Medication	Х	Х	Х	Х	Х	Х	Х	Х
MDS-UPDRS motor score	Х					Х		
Clinical Dyskinesia Rating Scale (CDRS)	Х					Х		
Motor symptom diary (3 days)	X					Χ	Χ	Х
Non-motor symptom checklist	Χ					Х	X	Х
Impulsive compulsive (QUIP)	Χ					Х		
Apathy scale Starkstein (AS)	X					Х		
Neuropsychological examination (incl. Mattis Dementia rating scale)	X					X		X
Mini-International Neuropsychiatric Interview	Х					Χ		
Psychiatric assessment	X					Х		
Hoehn and Yahr stage	X					X	Χ	Х
AMC disability scale (ALDS)	X					Х	X	Х
PDQ-39	X				Х	Х	X	X
EQ-5D	X	X	Х	Х	Х	Х	X	X
Treatment preference	X							
Treatment satisfaction						Х	Х	Х
Satisfaction with life scale	Х					Х	Х	X
Treatment failures		X	Х	Х	Х	Х	Х	Х
Side effects/adverse events/complications		X	X	Х	Х	Х	X	Х
Crossover to other treatment			Х	Х	Х	Х	Х	X
iMTA Medical Consumption Questionnaire (iMCQ)	X		X	X	Х	X	X	Х
iMTA Productivity Cost Questionnaire (iPCQ)	X		X	X	Х	Х	X	X
Use of (informal) care	Χ		X	X	X	X	Х	Х
Caregiver burden	Х		Χ	Χ	Χ	Χ	Х	X

Version 7: 23-10-2019 43 of 48

Table 2: assessment schedule patient preference trial

	Visit 1 Baseline	Visit 2 9mo		Visit 4 24mo	Visit 5 36 mo
Baseline characteristics	Х				=
Medication	X	Х	Х	Х	X
Hoehn and Yahr stage	Х				
PDQ-39	Х		Х	Х	X
Treatment preference	Х				
Treatment satisfaction			Х	Х	X
Side effects/adverse events/complications		Х	Х	Х	X
Treatment failures and cross-over		Х	Х	Х	X

Version 7: 23-10-2019 44 of 48

12.5 Cost Effectiveness analysis (CEA)

The economic evaluation of CLI against DBS treatment will be performed based on intention-to-treat as a cost-effectiveness and cost-utility analysis from a societal perspective with the costs per unit on the PDQ-39 and the costs per quality adjusted life-year (QALY) as the primary outcomes respectively. The primary outcome of the cost-effectiveness analysis is closely related to the primary clinical outcome, the PDQ-39. The cost-utility analysis is considered mandatory to enable health policy makers allocating scarce health care resources across disease populations, across interventions, and across health sectors, based on explicit efficiency criteria. It is expected that CLI generates higher costs than DBS during the year of follow-up and should therefore sufficiently pay off compared with DBS in terms of increased effectiveness in order to be affordable for patient populations that might benefit from both treatments. It is yet unclear whether CLI actually pays off sufficiently.

Incremental cost-effectiveness and cost-utility analyses will be performed for a willingness-to-pay value of €120,000 (for rationale, see sample size calculation) based on the net health benefit transformations of the respective incremental cost-effectiveness ratios and assuming reasonably normally distributed cost data. The time horizon in the study equals 1 year. With this time frame no discount rate will be applied for effects and costs to account for time preference. However, given the 5-year life-cycle of the studied devices (neurostimulator, tube, and pump) and the marked contrast of costs in the first year of treatment compared to subsequent years within the life-cycle period, we will depreciate the initial add-on intervention costs (placement of neurostimulator for DBS and tube and pump placement for CLI) over five years.

One-way and multi-way probabilistic sensitivity analyses will be performed for the length of the friction period (3-6 months), and choice of UK rather than Dutch tariffs of time trade-off ratings of health states.

Additional analyses will be performed with the assessments 24 and 36 months after start of treatment, to assess the longer term costs and benefits of both treatments more precisely.

Cost analysis

From the societal perspective the economic evaluation will include the direct medical as well as the direct and indirect non-medical costs of care. Indirect medical costs are not included as both treatments do not affect survival. All costs made by providers (index intervention and subsequent inpatient and outpatient health care), employers (loss of productivity due to absence from and impaired presence at work), patients (out-of-pocket

Version 7: 23-10-2019 45 of 48

expenses due to health care related travel, household assistance, over-the-counter medication) and their primary caregivers (non-reimbursable expenditures) will be quantified.

Unit costing will be in accordance with the most recent update of existing national guideline as much as possible.[21]. Costs will be price-indexed for the base year 2014. Yearly consumer price indices will be used to standardize unit costs estimated in different calendar years. Mean costs per patient over the period of the trial will be calculated.

Version 7: 23-10-2019 46 of 48

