5. TREATMENT OF SUBJECTS

5.1 Investigational product/treatment

CLI and DBS are both complex treatments and are therefore performed by teams that consist of various specialties (e.g. neurologist, neurosurgeon, gastroenterologist, and specialized nurses). In the Netherlands, 6 centres are permitted to perform DBS. Three of these also offer CLI, but in a much smaller number. CLI is performed in approximately 45 centres. For the study, CLI and DBS treatments should be optimally performed, i.e. by the best-trained teams. It is inevitable that the centres that perform the treatments at present perform the study-treatments as well. This implies that CLI and DBS will be carried-out in different centres. An advantage of this (Dutch) situation is that the study design closely resembles the current clinical practice, and as such the study results will be highly externally valid.

DBS treatment (Medtronic, Minneapolis, MN, USA)

Treatment is in accordance with the usual care regarding this procedure. For DBS, a neurosurgeon places two electrodes in the brain. These are connected to an implantable pulse generator. Patients are on average 4 days hospitalized. Patients do not receive PD drugs on the day of surgery until the end of the procedure. A stereotactic technique will be employed for implantation with the Leksell stereotactic frame (Elekta, Stockholm, Sweden) and guided by MRI. For this part of the surgery, patients will have local or general anaesthesia, both methods are possible in usual care and the surgeon will decide the method with the patient. The decision for electrode placement is based on MRI, microelectrode recordings and macro-electrode stimulation effects. A four contact electrode will be implanted in the subthalamic nucleus (STN). Subsequently, patients will have a second surgery under general anaesthesia to implant the pulse generator (ActivaPC or ActivaSC), subcutaneously in the subclavian area. The electrodes are connected to the pulse generator. During the course of the study, changes in drug treatment are allowed. Patients will regularly visit the outpatient clinic to adjust stimulation parameters and PD medication while assessing the interaction between both treatments.

CLI treatment (Duodopa, Abbott, Abbott Park, IL, USA)

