Treatment is in accordance with the usual care regarding this procedure. In CLI, a levodopa-gel is continuously administered through a tube in the jejunum. The CLI-gel is dispensed into cassettes connected to an ambulatory programmable pump that delivers the suspension. One cassette supplies 100 ml gel containing 2000 mg levodopa and 500 mg carbidopa that lasts — depending on the individual needs — on an average 16 hours.

Version 7: 23-10-2019 19 of 48

The pump and cassette weight approximately 0.5 kg. The initiation and dose adjustments of CLI require 5 to 12 days of hospitalization. In some centres, a temporary nasoduodenal tube is used to find out if the patient responds favourably to continuous levodopa infusion on day 1 to 3. On day 1 or 4 (depending on whether a temporary nasoduodenal tube is used first), a gastroenterologist endoscopically places a PEG tube in the stomach with an extension tube clipped in the jejunum using local anaesthetic and sedation with a short acting benzodiazepine. The tube is subsequently connected to the pump. Thereafter, CLI will immediately be continued and subsequently adjusted within the following days of inpatient stay. On day 5 to 12, the patient will be discharged. Patients will regularly visit the outpatient clinic to adjust the dose. Most patients use the pump only during daytime.

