The primary objective of the economic evaluation is to estimate the cost-effectiveness and cost-utility of CLI treatment versus DBS treatment in the first year of follow-up after treatment initiation. The results of the cost-effectiveness analysis (CEA) allow for local decision making on the economically most optimal treatment approach for patients with PD, based on the clinically relevant health outcomes regarding quality of life in particular, while the cost-utility analysis (CUA) provides information for health policy decision makers to decide upon efficient and affordable health care in general, based on nationally accepted evaluation criteria regarding costs per QALY in view of patients' disease burden.

Types of economic evaluation

The economic evaluation of CLI against DBS was conducted alongside the INVEST clinical trial with individual patient-level data. The costs per unit change on the PDQ-39 summary index score at 12 months follow-up versus baseline and the costs per quality adjusted life year (QALY) were the primary economic outcomes. Incremental cost-effectiveness (ICER) and cost-utility (ICUR) ratios were calculated as the costs difference divided by the difference in effect for CLI minus DBS treatment.

Jurisdiction

The trial was conducted in the Netherlands, where health insurance is obligated for inhabitants and health care is offered by public and private providers.

Perspective, time horizon and discounting

Both health care and societal perspectives were taken into account with a time horizon of 12 months following index surgery. Because the time horizon was 12 months, no discounting was performed.

Cost components

Costs encompassed health care costs, out-of-pocket expenses by patients and family members and costs of productivity loss due to sick leave from work (absenteeism) or lowered efficiency while at work (presenteeism).

Sources

Health care costs covered the use of the following use of resources:

- screening for appropriateness of treatment indication;
- index treatments CLI with infusion devices or DBS with stimulation devices;
- emergency departments visits;
- inpatient hospital admissions at neurology, psychiatry, the intensive care, or other units;
- outpatient hospital consultations (*e.g.*, medical specialist, specialist nurse);
- diagnostic procedures (*e.g.*, imaging by MRI, CT, ultrasonography or X-ray);
- therapeutic procedures (*e.g.*, ex-plantation, revision tube or other material, medication);

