If opportune, unit costs of (non-)hospital resources, working hours lost, and time spent on the patient by the primary care-giver were obtained from the most recent Dutch Manual on Costing in health care research (DMC).²³ The unit costs of the (re)placement of the neurostimulator system and of the tube and pump system (re)placements were based on unit costing sheets for distinct hospital care resources from the treatment center with the highest number of inclusions and subsequently capitalized based on a 5-year depreciation period (reflecting the lengths of their life cycles) in order to allow for a robust estimate of the difference in yearly treatment costs by study arm, irrespective of the chosen study's time horizon. The same hospital unit costing sheets, existing rates for mutual services excluding VAT, or passer-by prices (e.g., AMC Passantenprijslijst OZP, 2020) were used for observed diagnostic examinations and therapeutic procedures not listed in the DMC. Unit costs for medication were gathered from the Dutch Pharmaceutical Compass assuming standard prescriptions.^{26,27} The unit cost of lost working hours at the mean age of the included working patient at baseline was used, non-specific for gender. In case of prolonged continuous sick leave longer than the friction period, the friction cost method was applied.²⁸ The length of the friction period in days was calculated as the average over the study's observation period 2015-2020, weighted for the

yearly number of included patients, and equaled 97 days.^{23,29} Table EE1-S in the Supplementary Material shows unit cost of the resources used. Unit costs held for the base year 2020; unit costs originating from different calendar years were price-indexed with general yearly consumer price indices from Statistics Netherlands.³⁰

Costs of resources used were calculated by multiplying the frequency of distinct resources used with their respective (depreciated) unit costs. Volumes and costs (of health care used, out-of-pocket expenses, and productivity loss) are reported separately as (subtotal and total) means per patient per study arm.

Analyses were adjusted if deemed necessary in case of Parkinson-related or Parkinson non-related outliers in costs or QALYs. If related to Parkinson's disease, these were included and reported, if caused by unrelated comorbidities, these could have been excluded.

Health outcomes

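### Five-year spreading covers only device placement and replacement and names no interest rate, so the total yearly CLI-DBS cost difference still depends partly on the time horizon

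*Protocol*

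**What the plan says.** Protocol 12.5 sets a one-year horizon and states: "With this time frame no discount rate will be applied for effects and costs to account for time preference". It then makes an exception for start-up costs. Citing the five-year device life and "the marked contrast of costs in the first year of treatment compared to subsequent years within the life-cycle period", it says "we will depreciate the initial add-on intervention costs (placement of neurostimulator for DBS and tube and pump placement for CLI) over five years".

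The HEAP (Unit costs and costing) applies the rule to the unit costs of placing and replacing the neurostimulator system and the tube and pump system. These are "subsequently capitalized based on a 5-year depreciation period (reflecting the lengths of their life cycles"). The stated purpose is a "robust estimate of the difference in yearly treatment costs by study arm, irrespective of the chosen" horizon of the study. Under Perspective, time horizon and discounting it adds: "Because the time horizon was 12 months, no discounting was performed". No interest rate is given for the capitalization.

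Screening and inpatient admissions are separate cost components (HEAP, Sources). Costs are frequency times unit cost, with the unit cost depreciated where that applies. In Table EE1-S the asterisk is on the CLI pump, PEG placement, tube replacement and DBS (re)implantation. No screening row and no hospital-day row carries it. The planned sensitivity analysis on this point varies only the depreciation period, from 5 to 6, 7 and 8 years.

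**The concern.** The reason given for spreading is that year 1 is not typical of later years. That reason applies equally to the index admission, the screening work-up and the nasal-tube evaluation, which also occur once. If they are charged in full to the 12 months while the devices are spread, the total yearly difference mixes annualized and non-annualized start-up costs. The index stays differ between the arms: for CLI, "The initiation and dose adjustments of CLI require 5 to 12 days of hospitalization"; for DBS, "Patients are on average 4 days hospitalized".

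The second issue is time preference. A 12-month horizon is a reason not to discount flows within the year. It does not cover an outlay spread over five years, where dividing by five understates the equivalent annual cost.

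The cost difference is the numerator of both primary ratios and enters every net-health-benefit value. Protocol 12.5 also plans analyses at 24 and 36 months. Yearly figures from those would not be comparable with the 12-month figure if unspread start-up costs differ between arms.

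**Working it through.** **Inputs from the documents.** Planned yearly cost difference €34,174, willingness to pay €120,000 per QALY, SD 0.35 QALY and €10,000 (Protocol 4.4). Index stay 5 to 12 days for CLI and about 4 for DBS (5.1). DBS equipment and batteries €10,000 per patient-year (Protocol section 1).

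**Assumptions.** The unit-cost column of Table EE1-S is empty and no interest rate is given. I assume a ward day of €400 to €650, interest of 2.5 to 5%, and a DBS outlay of €20,000 to €50,000 (the upper end is 5 × €10,000).

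**1. The plan's own figure.** 34,174 / 120,000 = 0.2848 QALY (stated as 0.2847). The net-health-benefit SD at zero correlation is √(0.35² + (10,000/120,000)²) = 0.3598. The normal approximation gives 26 per group, and 26 / 0.8 gives 33 per group, 66 in total. The figure is reproduced. It does not use the depreciation rule, so the sample size is unaffected.

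**2. Dependence on the horizon.** Let R be recurrent yearly cost, K the spread one-off cost and A the unspread one-off cost. For a horizon of T years, up to five:

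mean yearly cost = R + K/5 + A/T.

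The K term does not change with T; the A term does. Moving from T = 1 to T = 5 changes the yearly CLI minus DBS difference by (1 − 1/5) × (A_CLI − A_DBS) = 0.8 × (A_CLI − A_DBS). From T = 1 to T = 3 the factor is 2/3. The total is horizon-free only if the net unspread cost is zero.

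**3. Admission part.** Extra CLI days: 5 − 4 = 1 to 12 − 4 = 8.

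| Case | 0.8 × days × price | Share of €34,174 | QALY at €120,000 |
|---|---|---|---|
| Low | 0.8 × 1 × 400 = €320 | 0.9% | 0.003 |
| Middle | 0.8 × 4.5 × 525 = €1,890 | 5.5% | 0.016 |
| High | 0.8 × 8 × 650 = €4,160 | 12% | 0.035 |

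**4. Interest part.** Equivalent annual share over five years = i / (1 − (1+i)^−5), against 0.200 for plain division:

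- 2.5%: 0.2152 (8% higher)
- 4%: 0.2246 (12% higher)
- 5%: 0.2310 (15% higher)

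These assume year-end charges. With charges at the start of each year the shares are divided by 1 + i, giving 0.210 to 0.220. The gap grows in the planned longer-life analysis: at 8 years and 4% the share is 0.149 against 0.125.

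Taken gross on DBS, the shortfall is 20,000 × 0.0152 = about €300 to 50,000 × 0.0310 = about €1,550 a year. The effect on the difference is (share − 0.2) × (K_DBS − K_CLI), so the same correction to the CLI pump, PEG and tube must be subtracted. K_CLI is not given.

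**5. Direction.** On the asterisk reading:

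- Raises CLI minus DBS: the longer CLI admission charged in full; omitted interest, but only if the DBS outlay is the larger.
- Lowers it: MRI of the brain in screening, which Table EE2a marks as not applicable for CLI; DBS electrode replacement, cable replacement and battery exchange, which have no asterisk, while CLI tube replacement has one.

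Without unit costs and frequencies these cannot be netted.

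**6. Scale against sampling error.** The planned standard error of the net-health-benefit difference is 0.3598 × √(2/26) = 0.10 QALY. Even the two upper ends together, 4,160 + 1,550 = €5,710, are 0.048 QALY, under half a standard error.

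**The case against.** No sentence says that the index admission and screening are charged wholly to year 1. That is inferred from missing asterisks, and the footnote explaining the asterisk breaks off in the text as read, which cannot be held against the plan. The procedure rates might already include bed days. This stands as a limit on certainty. Year-1 charging is still the most natural reading, because hospital days have their own per-day price and the HEAP names only device-system placement and replacement for spreading.

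A zero interest rate is likewise not spelled out. The HEAP leaves its capitalization formula undefined, and the no-discounting sentences refer to the 12-month horizon. With no rate named and discounting declined, undiscounted division is the likely calculation, but it is not a declared rule.

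The horizon claim may be meant only for the index-treatment cost line. If so, it is correct for that line apart from interest, and only the total difference is affected.

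Expensing bed days while spreading durable equipment is a coherent convention, and the protocol ties its rule to device life. For that reason full spreading of bed days is not proposed here as the base case.

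The separate reporting of screening, stay and device costs, and the planned later analyses, help a reader see the one-off items. Neither tests what is spread or at what rate.

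**Conclusion.** The point holds in a limited form. As the plan most naturally reads, start-up costs other than the devices fall in year 1, so the total yearly difference is not independent of the horizon. An undiscounted one-fifth share is also below the equivalent annual cost. The planned 6-to-8-year analysis tests neither.

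The admission part is €320 to €4,160 a year on assumed ward-day prices; the top end needs every CLI patient to stay 12 days at the highest price. The interest part is smaller and must be taken net of CLI equipment. Both are modest against the planned sampling error.

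A reader might infer that the rule favours the trial's hypothesis by inflating the CLI minus DBS difference. The documents do not support that: items push in both directions, their prices and frequencies are not given, and the net sign is unknown. Nor do they support saying that the plan expressly charges these costs in full to year 1 or expressly sets a zero interest rate. This is a worthwhile, cheap improvement to the costing rule and does not invalidate the evaluation.

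**What to change.** In the HEAP:

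- (a) Compute the yearly device and placement charge as an equivalent annual cost: an annuity over device life at a stated rate, with the timing convention given. Keep the undiscounted version as a sensitivity analysis.
- (b) Add to the 6-to-8-year depreciation analysis a sensitivity analysis that spreads all one-off index costs (screening, nasal-tube evaluation, index admission days) by the same rule in both arms. State whether the PEG and (re)implantation rates already include bed days, so that days are not counted twice.
- (c) Limit the statement about independence from the horizon to the costs actually spread. Make the spread items in the text and in Table EE1-S agree, including electrode, cable and battery items.

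The cost is some HEAP wording, one formula, a flag for index-admission days in data already collected, and one extra analysis run. The reported cost difference will change modestly, in a direction that cannot be predicted from the documents.
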